PI	Principal Investigator
SAE	serious adverse event
SAH	S-adenosylhomocysteine
SAM	S-adenosylmethionine
SCQ	Social Communication Questionnaire
SRS	Social Responsiveness Scale
THF	tetrahydrofolate

PROTOCOL SYNOPSIS

TITLE	An examination of changes in urinary metabolites with use of folinic acid in children with autism spectrum disorder (ASD)
SPONSOR	[name]
FUNDING ORGANIZATION	Gift Funded from the JS Foundation
NUMBER OF SITES	1
RATIONALE	
Children with autism spectrum disorder (ASD) have been found to have impaired transport of folate across the blood-brain barrier due to folate receptor auto-antibodies (FRAA) that either block or bind to the folate receptor alpha (FR alpha). This creates the condition known as “cerebral folate deficiency” where serum folate concentrations are normal but CSF folate concentrations are low. Recent studies have found that supplementing children with ASD with a reduced form of folate – folinic acid – allows for bypass of the impaired folate transport mechanism into the CSF, leading to improved behavior and language development. We propose to further examine this exciting new therapeutic possibility by conducting an open-label study of folinic acid in children with ASD to examine both changes in behavior and correlations with urinary metabolites.
 
We previously created an outcomes database within a school for children with ASD (Oak Hill School, San Anselmo, CA) to carefully track teacher and parent-rated assessments of children enrolled in the school. In a prior study, we established the ability to provide a treatment (the phytochemical, sulforaphane) to children in the school while monitoring changes in urinary metabolites and clinical outcomes. This study found that changes in specific urinary metabolites were associated with clinical improvements, which suggested specific metabolic pathways that are involved in the treatment response. In the current study, we will use the same successful model to determine if changes in urinary metabolites are correlated with clinical changes. This study may provide insight into the mechanism of action of folinic acid and may allow for the development of a biomarker prediction model that will determine which children are most likely to benefit from this treatment.

STUDY DESIGN	Open label treatment study elucidating mechanism of action.
PRIMARY OBJECTIVE	To examine changes in urinary metabolites in children with ASD being treated with folinic acid and to determine if changes in urinary metabolites are correlated with clinical improvements.
SECONDARY OBJECTIVES	Develop a prediction model to determine which children are most likely to benefit from folinic acid.

NUMBER OF SUBJECTS	40
SUBJECT SELECTION CRITERIA	
Inclusion Criteria: Age 5-22, enrolled at Oak Hill School, diagnosis of autism established by DSM-IV criteria and clinician examination.
 
Exclusion Criteria: Seizure disorder, serious medical illness within the last 6 months as judged by the study PI. Known allergy to folate.

TEST PRODUCT, DOSE, AND ROUTE OF ADMINISTRATION	Folinic acid 2mg/kg per day (maximum 50mg/day) in two equally divided doses with half the target dose given during the first 2 weeks.
CONTROL PRODUCT, DOSE AND ROUTE OF ADMINISTRATION	There is no control product in this study.
DURATION OF SUBJECT PARTICIPATION AND DURATION OF STUDY	
Subjects will be on study for 4.5 months
 
Screening: up to 2 weeks.
 
Treatment: 3 months
 
Follow-up: 1 month (1 additional month after treatment)
 
The total duration of the study is expected to be 12 months. 3-6 months for subject recruitment; 4 months for final subject follow-up; 2 months for data analysis and manuscript preparation.

CONCOMITANT MEDICATIONS	
Allowed: all
 
Prohibited: none

EFFICACY EVALUATIONS	
Parent (Aberrant Behavior Checklist, Social Responsiveness Scale, Pediatric Quality of Life)
 
Teacher (Student Progress Form, Aberrant Behavior Checklist, Social Responsiveness Scale)
 
Urinary Metabolomics (Baseline and 3 months)

PRIMARY ENDPOINT	
 Correlation between mean change in Aberrant Behavior Checklist and mean change in urinary metabolites.
SECONDARY ENDPOINTS	
 Correlations between changes in urinary metabolites and all secondary outcome measures.
OTHER EVALUATIONS	None

SAFETY EVALUATIONS	All study subjects are enrolled at the Oak Hill School and will be observed all school days by teachers, who are aware of student participation in the study. Parents, teachers, and enrolled students will be advised to report any new medical problems to study investigators, who will evaluate all potential adverse events and report to the CHR according to established guidelines.
PLANNED INTERIM ANALYSES	No interim analyses planned given the short-term duration of the study, the established safety of the treatment, and the lack of randomization (so no ability to compare rates of AE's between active and placebo treatment).
STATISTICS Primary Analysis Plan	Correlations between changes in mean levels of urinary metabolites and changes in mean behavioral measures (0 to 3 months) will be done using a spearman rank correlations test using STATA. We prospectively define correlations with an absolute value of ≥ 0.6 to be potentially involved in the mechanism of action. All metabolites with this correlation will be mapped to known metabolite pathways to examine pathway changes.
Rationale for Number of Subjects	We are recruiting all children currently enrolled at Oak Hill School (current enrollment = 36). We anticipate that we will enroll 20 students in the current study, but we will allow up to 40 (if school enrollment increases).

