In summary, children with ASD are known to have a high prevalence of cerebral folate deficiency, likely caused by folate receptor auto-antibodies (FRAA), which block the normal transfer of folate from the bloodstream to the CSF. Prior studies have documented that supplementation with reduced forms of folate can bypass the impaired transport mechanism and restore normal cerebral folate levels. A recent randomized controlled trial found that folinic acid supplementation improved language and behavior in children with ASD. We therefore propose to conduct an open-label study of folinic acid in children with ASD to determine if clinical improvements are correlated with changes in metabolites known to be related to the folate pathways. This study will gain information needed to determine a possible metabolomic mechanism of action of folinic acid and allow for the development of a prediction model to identify children with ASD who are mostly likely to respond to treatment.

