8.2 Clinical Laboratory Measurements

Urinary Metabolomic Profile – all participants will have urine collected (fasting, 8am target collection time) at Screening and Close-out (3 months). Urine will be stored in sterile containers at -80 degrees Celsius and analyzed in one batch after all participants have completed the study. Metabolomic assessment will be conducted by Metabolon (Research Triangle, NC). Metabolon is one of the largest and most established laboratories conducting state-of-the art metabolomics assessments of urine, plasma, and other clinical samples. Metabolon has 160 employees including more than 40 PhDs with diverse backgrounds in molecular biology, biochemistry, bioinformatics, and statistics. They have completed over 4,000 metabolomic projects for over 700 clients. Their analyses have been used in more than 500 peer-reviewed publications including numerous articles in *Cell*, *Nature*, and *Science*. (www.metabolon.com)

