13.1 Analysis of Primary Endpoint

The primary analysis in the study is the correlation between the mean change in each urinary metabolite and the mean change in participant behavior as measured by the ABC using the spearman rank correlation test in Stata. The primary outcome measure is the correlation between urinary metabolites and the total ABC score.

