13.3 Sample Size

The study is designed to detect a correlation coefficient (Pearson's r) between the mean urinary metabolite change and the mean behavioral measure change of 0.6, which is considered to indicate a moderate-to-strong correlation. Using a two-sided alpha of 0.05 and a Beta of 0.1 (90% power), our required sample size is 25 participants to detect this degree of correlation. Since we may incur up to 20% dropout (5 participants), our target sample size is 30 participants, but we will allow up to 40 to provide the study opportunity to all children enrolled in the target school (Oak Hill School).

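### The plan maps every metabolite with |rho| ≥ 0.6 to pathways but never gauges how many would pass by chance; this matters near the anticipated 20 children and little at the design size of 25

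*Combined protocol and SAP*

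**What the plan says.** The Statistics row of the synopsis sets the rule. Changes from 0 to 3 months are compared by Spearman rank correlation, an absolute correlation of at least 0.6 is taken "to be potentially involved in the mechanism of action", and then: "All metabolites with this correlation will be mapped to known metabolite pathways to examine pathway changes". The cut-off stands only there. Section 13.1 gives the test, "the correlation between the mean change in each urinary metabolite" against change in total ABC, with no selection rule. Section 13.3 uses 0.6 as a design effect size (Pearson).

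The sample-size figures differ:
- Synopsis: "We anticipate that we will enroll 20 students in the current study", with up to 40 allowed and 36 currently enrolled at the school.
- Section 13.3: "our required sample size is 25 participants to detect this degree of correlation". After allowing for up to 20% dropout, "our target sample size is 30 participants".

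Section 8.2 names the metabolomics laboratory but gives no number of metabolites. Section 13.2 calls the study exploratory and makes no multiplicity adjustment. Section 13 promises a detailed SAP before the final analysis. No section mentions an expected number of chance passes, a permutation reference, a false-discovery estimate or a comparison of observed with expected counts.

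**The concern.** The synopsis describes the design as one that elucidates mechanism, and the pathway map is where that evidence would appear. A fixed correlation cut-off applied to a broad panel in a small sample lets some unrelated metabolites through, and these would be placed on pathways alongside any real ones. Without a reference count, a map built from, say, five metabolites cannot be read: it might be well above chance or just what chance delivers.

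A reader who is later told the panel size and the number of children could work out the average chance count. That reader could not work out how widely the count varies, because this depends on how strongly the metabolites correlate with one another, and only the trial's own data show that.

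**Working it through.** **1. The plan's own figure.** Required n for r = 0.6, two-sided alpha 0.05, 90% power, by Fisher's z:

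n = ((1.960 + 1.282) / atanh(0.6))² + 3 = (3.242 / 0.693)² + 3 = 24.87, rounded up to 25. Section 13.3 is reproduced. That calculation covers the power of a single test. It says nothing about how many of many metabolites pass the 0.6 cut-off.

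**2. Number of children.** The count that matters is children with paired urine and outcome data, not children enrolled. With the plan's maximum 20% dropout:
- 20 anticipated: 20 × 0.8 = 16
- 30 targeted: 30 × 0.8 = 24

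**3. Chance rate per metabolite.** The probability that |rho| ≥ 0.6 when there is no association was taken from 4,000,000 random permutations at each n, without ties. As a cross-check, t = 0.6 × √((n − 2) / 0.64) on n − 2 degrees of freedom gives somewhat lower values: 0.52% at n = 20, 0.15% at n = 25 and 0.046% at n = 30.

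**4. Expected chance passes = panel size × rate**, for one behavioural outcome. All panel sizes are assumptions. The column for 30 stands for a short folate-pathway list.

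| Paired children | Rate | 30 | 100 | 500 | 1,000 |
|---|---|---|---|---|---|
| 16 | 1.58% | 0.47 | 1.6 | 7.9 | 15.8 |
| 20 | 0.60% | 0.18 | 0.6 | 3.0 | 6.0 |
| 24 | 0.23% | 0.07 | 0.23 | 1.2 | 2.3 |
| 25 | 0.18% | 0.06 | 0.18 | 0.9 | 1.8 |
| 30 | 0.06% | 0.02 | 0.06 | 0.3 | 0.6 |

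At n = 36 and n = 40 the counts per 500 are 0.08 and 0.03. Put the other way, one chance pass is expected once the panel reaches 1/rate: about 63 metabolites at n = 16, 165 at n = 20 and 540 at n = 25.

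**5. Spread.** Correlation between metabolites leaves the mean unchanged but widens the distribution. For 500 metabolites, the second column below assumes one common factor carrying 30% of the variance:

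| Paired children | 95th percentile, independent | 95th percentile, common factor |
|---|---|---|
| 16 | 13 | 26 |
| 20 | 6 | 11 |
| 25 | 3 | 4 |
| 30 | 1 | 2 |

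The same correlation lowers the probability of at least one chance pass, from 0.95 to about 0.77 at n = 20 and from 0.60 to about 0.41 at n = 25. Chance passes then come less often but in larger clusters.

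**6. More than one outcome.** The synopsis applies the rule to behavioural measures in the plural, Section 13.2 adds SRS and PedsQL, and Appendix 1 schedules ABC and SRS for both parents and teachers. If all five of these scales feed the map, expected chance pairs of metabolite and outcome at n = 20 with 500 metabolites are 5 × 3.0 = 15. The plan does not say which outcomes the map draws on.

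**The case against.** The strongest case is that the cut-off already does the filtering. At the design size of 25 its chance rate is 0.18%, about 27 times stricter than 0.05 (0.05 / 0.00184), and fewer than one chance pass is expected per 500. Reconciling the anticipated 20 with the required 25 and target of 30 would remove most of the problem. The label is hedged, the study is declared exploratory, a SAP is promised, and no planned decision turns on the count. The headline figures also rest on an assumed panel size.

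Much of this stands. It is why the severity is low, and why the counts are given over a range of panel sizes. It does not remove the point. Twenty is the plan's own expectation, and dropout would take it lower. Declining to adjust is no reason to omit the chance count, and the permutation leaves the list as it is. A promised SAP is the right place for the remedy but does not yet contain it.

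A reader might infer three stronger things, none of which the documents support:
- *That some stated share of the map will be false.* The number of true signals is unknown, so no share can be given.
- *That the unadjusted screen is an error.* It is a declared choice for exploratory work.
- *That the plan contradicts itself on which metabolites are screened.* The Background summary speaks of aiming "to determine if clinical improvements are correlated with changes in metabolites known to be related to the folate pathways", but that is motivation. The operative text in Section 13.1 covers each metabolite.

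**Conclusion.** The concern holds as a gap in what will be reported, not as a flaw in the test or the cut-off. As written, the study will produce a pathway map with no means of saying whether it exceeds chance. The size depends on two quantities the plan leaves open: the panel size and the number of children with paired data. On an assumed panel of 500 and one outcome, the gap is material at 16 to 20 paired children and minor at 24 to 30. With a short listed set of metabolites it is small at any of these sizes.

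The rates assume no ties. The 95th percentiles under correlation rest on the assumed 30% common factor and show only that the spread cannot be read from the mean. The figure for 16 children assumes that the full 20% dropout occurs and costs paired data; Section 11 asks children who stop the supplement to continue outcome assessments, so the loss could be smaller. Low severity: a cheap improvement.

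**What to change.** In the SAP promised in Section 13, or in Section 13.1 with the synopsis rule carried over:

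- Keep the 0.6 cut-off and the unadjusted list. Remove no metabolite because of the count.
- State which outcomes feed the pathway map, including which rater's ABC total is primary, and which metabolites are screened.
- Permute each child's whole set of outcome changes across children, for example 1,000 times, with every metabolite profile kept intact. Rerun the same screen each time for every outcome that feeds the map. An ABC-only permutation would understate chance passes if other outcomes contribute.
- Report the mean and 95th percentile of chance passes, per outcome and for the map as a whole, beside the observed count, the panel size and the number of paired children.
- Describe the map as exceeding chance only if the observed count lies above that range.

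The cost is a few lines of text and a few hours of analysis on data already planned, with no new visits or samples. The downside is a map that may look less convincing. Equally, an observed count clearly above the chance range would strengthen the mechanistic reading.

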1 BACKGROUND

1.1 Overview of Clinical Studies

Cerebral folate deficiency in ASD: Prior studies have linked abnormalities in the metabolism of folate, an essential B vitamin, to ASD.¹ These abnormalities may relate to the ability of a child with ASD to transport folate across the blood-brain barrier. Children with ASD have been found to have impaired transport of folate across the blood-brain barrier due to auto-antibodies that either block or bind to the folate receptor alpha (FR alpha). (The antibodies are known as folate receptor auto-antibodies - (FRAA)). This creates the condition known as “cerebral folate deficiency” which describes an individual with normal serum folate concentrations but low concentrations of folate in the cerebrospinal fluid (CSF) due to impaired ability to transport folate across the blood-brain barrier.²

High prevalence of FRAA in ASD: Children with ASD have been found to have a high prevalence of FRAA. In a study of 93 children with ASD, 60% had blocking FRAA, and 44% had binding FRAA.³ Blocking antibodies interfere with binding of folate to the FR alpha and binding antibodies bind to the FR alpha and cause an antibody-mediated immune reaction. The rates of FRAA in ASD are higher than the 4-15% prevalence reported in healthy adults and the 3% prevalence reported in developmentally delayed non-autistic children.² Up to 23% of children with ASD who underwent lumbar puncture were reported to have abnormally low CSF folate concentrations.⁴ Together, this evidence suggests that low CSF folate levels may contribute to the abnormal physiology and clinical symptoms of ASD.

Reduced forms of folate can bypass impaired folate transport across the blood-brain barrier: Folinic acid, a reduced form of folate, is able to bypass the normal blood-brain barrier transport mechanism and increase CSF folate levels through a secondary transport mechanism that involves a reduced-folate transporter. Case reports have found that high-dose folinic acid supplementation markedly improves CSF folate levels in children with ASD and low CSF folate.²

Folinic acid supplementation improves language and aberrant behavior in ASD: In a recent (2016) randomized controlled trial of folinic acid supplementation vs. placebo in 48 children with ASD and language delay, children randomized to folinic acid had statistically significant improvements in language and aberrant behavior.² Furthermore, improvements were greater in the subgroup of children who were positive for FRAA, suggesting that children with more severe cerebral folate deficiency were more likely to benefit (FRAA was used a proxy for CSF folate levels, since it was not possible to obtain CSF folate on study participants due to the invasive nature of obtaining CSF).

Folate may support the 3 interdependent pathways involved in folate (THF)-dependent methionine transmethylation/transsulfuration metabolism. These pathways are involved in DNA synthesis, cellular methylation, and redox homeostasis, and an adequate cerebral supply of folate may allow for improved functioning of these pathways and clinical improvements.

[figure not shown]

Figure 1. This is an overview of the 3 interdependent pathways involved in folate (THF)-dependent methionine transmethylation/transsulfuration metabolism. The vital importance of these three interconnected pathways is underscored by their essentiality for error-free DNA synthesis (Folate Cycle Pathway 1); for cellular methylation (epigenetic) capacity (Transmethylation Pathway 2); and for the maintenance of glutathione (GSH) redox homeostasis (Transsulfuration Pathway 3). Because these 3 pathways regulate the distribution of precursors for DNA synthesis (proliferation), DNA/histone methylation (epigenetics) and glutathione synthesis (redox/antioxidant status), the homeostatic balance between these pathways is essential to support normal cell programming and ontogeny during prenatal and post-natal development.

In summary, children with ASD are known to have a high prevalence of cerebral folate deficiency, likely caused by folate receptor auto-antibodies (FRAA), which block the normal transfer of folate from the bloodstream to the CSF. Prior studies have documented that supplementation with reduced forms of folate can bypass the impaired transport mechanism and restore normal cerebral folate levels. A recent randomized controlled trial found that folinic acid supplementation improved language and behavior in children with ASD. We therefore propose to conduct an open-label study of folinic acid in children with ASD to determine if clinical improvements are correlated with changes in metabolites known to be related to the folate pathways. This study will gain information needed to determine a possible metabolomic mechanism of action of folinic acid and allow for the development of a prediction model to identify children with ASD who are mostly likely to respond to treatment.

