3 STUDY OBJECTIVES

3.1 Primary Objective

The primary objective is to determine if there is a correlation between changes in behavior and changes in urinary metabolites in children with ASD who receive folinic acid treatment for 12 weeks. This will provide insight into the potential mechanism of action.

3.2 Secondary Objectives:

Secondary objectives include an examination of the correlation between changes in urinary metabolites and other outcome measures, including the Social Responsiveness Scale (SRS) (parents and teachers) and the Pediatric Quality of Life Inventory (PedsQL) (parents). It is possible that specific urinary metabolites are related to different clinical domains, and we will therefore examine correlations in each of these domains.

STUDY DESIGN

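### The folate-pathway question behind the study has no pre-specified metabolite set, no set-level test and no rule for the administered compound

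*Combined protocol and SAP*

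**What the plan says.** The closing summary of Section 1.1 states a directed question: the study is "to determine if clinical improvements are correlated with changes in metabolites known to be related to the folate pathways". Earlier in that section the plan says "Folate may support the 3 interdependent pathways involved in folate (THF)-dependent methionine transmethylation/transsulfuration metabolism", and the Figure 1 legend names them as the folate cycle, transmethylation and transsulfuration. No urinary analytes are listed for any of the three.

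The formal text is more general. Section 3.1 says: "The primary objective is to determine if there is a correlation between changes in behavior and changes in urinary metabolites". Section 13.1 says: "The primary analysis in the study is the correlation between the mean change in each urinary metabolite and the mean change in participant behavior", using Spearman correlation and the total ABC score. The synopsis (Statistics, Primary Analysis Plan) adds the decision rule: "We prospectively define correlations with an absolute value of ≥ 0.6 to be potentially involved in the mechanism of action". The only pathway step follows it: "All metabolites with this correlation will be mapped to known metabolite pathways to examine pathway changes".

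On the assay, Section 8.2 says "Metabolomic assessment will be conducted by Metabolon (Research Triangle, NC"). It does not give the number of metabolites or say whether the assay is targeted. Section 13.2 calls the study exploratory and makes no multiplicity adjustment. Section 13 promises a detailed SAP before the final data are analysed.

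**The concern.** The background asks about particular pathways, but the analysis gives every metabolite the same standing and assigns pathways after the hits are known. Two things are missing as a result.

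First, nothing says in advance which metabolites belong to the three pathways, or how their results combine into an answer. If a few of many metabolites pass 0.6 and one can be linked to the folate cycle, methylation or transsulfuration, a reader cannot tell how far that link was chosen after the fact. If none passes, the plan does not say what follows.

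Second, the 0.6 rule does not separate a downstream response from the dose. If folinic acid is on the panel, its change over three months could reflect how much was taken. Section 7 has no control and no blinding, so families who give the supplement more reliably might also rate improvement more favourably. A correlation arising that way would be mapped to the folate cycle and could look like support for the mechanism.

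**Working it through.** **Inputs from the plan.** Cut-off 0.6 and anticipated enrolment 20 (synopsis). Required size 25, two-sided alpha 0.05, 90% power, r = 0.6 (Section 13.3). **Assumed, because the plan does not give them:** a panel of 200, 500 or 1000 metabolites, a folate set of 10 or 20, and independent metabolites.

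**1. The plan's own figure.** By Fisher's z, n = ((1.960 + 1.282)/atanh(0.6))² + 3 = (3.242/0.693)² + 3 = 24.87, rounded up to 25. This reproduces. It applies to one correlation, not to a panel or a pathway set.

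**2. Chance that one unrelated metabolite passes.** With no association and no ties, the ranks are a random permutation and rho = 1 − 6Σd²/(n(n² − 1)). At n = 20, n(n² − 1)/6 = 1330, so passing means Σd² ≤ 532 or ≥ 2128. Simulated permutations give q ≈ 0.0061 at n = 20 and q ≈ 0.00187 at n = 25.

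**3. Chance passes among m unrelated metabolites.** The expected number is mq, and P(at least one) = 1 − (1 − q)^m.

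| m | n = 20: expected | n = 20: P(≥1) | n = 25: expected | n = 25: P(≥1) |
|---|---|---|---|---|
| 10 | 0.06 | 0.06 | 0.02 | 0.02 |
| 20 | 0.12 | 0.12 | 0.04 | 0.04 |
| 200 | 1.2 | 0.71 | 0.4 | 0.31 |
| 500 | 3.1 | 0.95 | 0.9 | 0.61 |
| 1000 | 6.1 | >0.99 | 1.9 | 0.85 |

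For example, 1 − 0.9939^200 = 0.71. The expected counts do not need independence; the probabilities do.

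**4. What an empty folate set would mean.** In simulation, a metabolite with true r = 0.6 passes the cut-off with probability 0.447 at n = 20 and 0.438 at n = 25. In a set of 20 the chance of no hit at all is then:
- one true signal, n = 20: 0.553 × 0.9939^19 = 0.49
- one true signal, n = 25: 0.562 × 0.99813^19 = 0.54
- two true signals, n = 20: 0.553² × 0.9939^18 = 0.27
- two true signals, n = 25: 0.562² × 0.99813^18 = 0.31

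A count of hits, even within a named set, is therefore not a usable yes-or-no answer.

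**5. The administered compound.** This part is reasoning from the text, with no figure. The synopsis rule covers any metabolite that reaches 0.6. No section excludes or labels the study product. Capsule counts (Section 7.2.1) and the diary and bottle count at the three-month visit (Section 9.4) record adherence, but no analysis links them to the correlations. How often the compound would pass cannot be computed from the documents.

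**The case against.** The best defence is that objective and analysis agree. The synopsis and Sections 3.1, 4.1 and 13.1 all speak of urinary metabolites without restriction, the synopsis describes repeating an earlier discovery study at the same school, and Section 13.2 calls the work exploratory. The mismatch is with the background rationale, not with the formal objective. That stands, and it is a reason to keep the full screen rather than replace it.

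A reader might infer more than the documents support:
- **That the folate hypothesis is never tested.** Any folate-pathway metabolite the laboratory measures is correlated with ABC change and, if it passes, mapped. What is missing is the defined set and a test at that level.
- **That the panel is untargeted.** Section 8.2 does not say so.
- **That naming the set makes individual folate hits more trustworthy.** The same metabolites face the same cut-off either way. The table contrasts the whole panel with the set; it does not show folate hits improving.
- **That the drug's own products will pass as mechanism.** The plan does not say that folinic acid is measured, and the rule says only potentially involved. Folinic acid and its direct products may also belong to the folate cycle, so simply excluding them has no clear dividing line.

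Finally, the SAP promised in Section 13 could still name the set. That is true, but nothing in the current text commits it to do so.

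**Conclusion.** The point holds as a gap in pre-specification. As written, the plan cannot give a pre-defined answer, with a controlled error rate, to the question in Section 1.1. At the anticipated 20 participants the full screen would be expected to pass about 1 to 6 unrelated metabolites for panels of 200 to 1000, with a chance of at least one of about 0.71 to above 0.99. For a pre-named set of 10 to 20 that chance is about 0.06 to 0.12. These figures rest on assumed panel and set sizes and on independence. Correlation among metabolites would alter the probabilities but not the expected counts.

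The missing rule for the administered compound is plain from the text, but its effect depends on whether folinic acid is on the panel and cannot be sized. Nothing here shows the sample size of 25 to be wrong for the single correlation it addresses.

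**What to change.** Before assay data are opened, obtain the laboratory's analyte list and write the following into the SAP:

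1. List by name the measured metabolites belonging to the three pathways in Section 1.1.
2. Keep the full-panel 0.6 screen as the general analysis and label it exploratory.
3. Add one set-level test of the folate set against total ABC change. One suitable form permutes ABC change across children, with the mean squared Spearman rho over the set as the statistic, at the 0.05 level of Section 13.3. Permuting children preserves the correlation among metabolites, so the error rate does not depend on independence. Parents and teachers both complete the ABC, so state which total score is used.
4. Report every rho in the set with a confidence interval, including those below 0.6.
5. If folinic acid is on the panel, flag it as an exposure marker and show the set result with and without it.

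Record and date the addition on the registry. Section 13 commits to noting modifications before the first enrolment, so say so if enrolment has already begun.

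The cost is one list, some SAP text and a little more analysis; no new samples or participants are needed. Section 8.2 assays all urine in one batch after participants finish, which leaves time. The limitation to state is that a non-significant set test at 20 to 25 participants would not exclude involvement of one or two metabolites.
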